#### 7.4. Laboratory Procedures

Not applicable.

### 8. SUBJECTS COMPLETION/WITHDRAWAL

#### 8.1. Completion Criteria

Subjects are considered to have completed the study if they:

- provided informed consent
- they are eligible
- completed all study visits
- have not withdrawn/discontinued from the study for any reason described in Section 8.2

#### 8.2. Withdrawal/Discontinuation from the Study

A subject will be withdrawn from the study for any of the following reasons:

- Subject death during the study period
- Subject withdrawal of consent
- Subject not compliant to protocol in the opinion of the Principal Investigator
- Subject lost to follow-up
- Subject no longer meets eligibility criteria (e.g. the subject becomes pregnant)
- Subject develops significant or serious adverse events causing discontinuation of contact lens wear
- Subjects who have experienced a Corneal Infiltrative Event (CIE)

- Investigator's clinical judgment regarding the subject safety reasons (that it is in the best interest of the subject to stop treatment)
- Subject missed two study visits
- Subject not compliant with lens wear schedule

For discontinued subjects, the Investigator will:

- Complete the current visit (scheduled or unscheduled)
- Complete the Final Evaluation, indicating the reason that the subject was discontinued from the study

An additional subject will be enrolled if a subject discontinues from the study prematurely.

In cases where a subject is lost to follow-up, every possible effort must be made to contact the subject and determine the reason for discontinuation/withdrawal. The measures taken to follow up must be documented including two written attempts and a certified letter (or equivalent) as the final attempt.

## **9. PRE-STUDY AND CONCOMITANT INTERVENTION/MEDICATION**

Concomitant medications will be documented during screening and updated during the study. Disallowed medications or therapies for this study include: any topical medication such as eye drops or ointment or any medications that in the opinion of the investigator would affect contact lens wear.

## **10. DEVIATIONS FROM THE PROTOCOL**

Investigator will notify study sponsor upon identification of a protocol deviation. Major protocol deviations must be reported to the sponsor within 24 hours after discovery of the protocol deviation. The Investigator will report deviations per IRB/IEC requirements. All deviations will be tracked and corrective actions implemented as appropriate.

If it becomes necessary for the Investigator to implement a deviation in order to eliminate an immediate hazard to the trial subject, the Investigator may implement the deviation immediately without notification to the sponsor. Within 24 hours after the implemented deviation, the Investigator must notify and provide the rationale to the Sponsor and, as required, the IEC/IRB.

## **11. STUDY TERMINATION**

The occurrence of one or more Unanticipated Serious Adverse Device Effect (USADE), or any SAE where the relationship to study agent cannot be ruled out, may result in stopping further study procedures. In the event of a USADE or SAE, the Sponsor may unmask the treatment regimen for the subject(s) and will discuss this with the Investigator before any further subjects are enrolled.

The Sponsor will determine when a study will be stopped. The Principal Investigator always has the discretion to initiate stopping the study based on patient safety or if information indicates the study's results are compromised.

JJVC reserves the right to terminate the study at any time for any reason. Additionally, the IEC/IRB reserves the right to terminate the study if an unreasonable risk is determined. The study can be terminated by the Principal Investigator at the individual clinical site due to specific clinical observations, if in their opinion, after a discussion with JJVC, it is determined that it would be unwise to continue at the clinical site.

JJVC (and the IEC/IRB and DMC, if applicable) will evaluate all adverse events. If it is determined that an adverse event presents an unreasonable risk, the investigation, or that part of the investigation presenting the risk, will be terminated, as soon as possible.

Should the study be terminated (either prematurely or as scheduled), the Investigator will notify the IEC/IRB and Regulatory Authority as required by local regulatory requirements.

## **12. PROCEDURE FOR HANDLING PRODUCT QUALITY COMPLAINTS**

A Product Quality Complaint (PQC) refers to any written, electronic, or oral communication that alleges deficiencies related to the identity, quality, durability, reliability, safety, effectiveness or performance of test articles after they have been released for clinical trial use.

Potential complaints may come from a variety of sources including but not limited to subjects, clinical research associates (CRA), clinical operations managers (COM), medical monitors, and site personnel, etc. The following are not considered product quality complaints:

- Subject satisfaction inquiries reported via "Subjective Questionnaires" and "Patient Reported Outcomes (PRO)"
- Clinical test articles that are stored improperly or damaged after receipt at the investigational site
- Lens replacements that occur due to drops/fall-outs
- Damage deemed by clinicians or clinical staff to be caused by handling by the user, and not indicative of a quality deficiency (i.e. tears, rips, etc.), only in situations where there is no deficiency alleged by the subject

Within 24 hours of site personnel becoming aware that a PQC has occurred, the PQC must be recorded in the EDC system, which will trigger an automatic email notification to the appropriate COM/CRA and Clinical QA representative. In cases where the EDC system in use is not configured to send automatic notifications or when an EDC system is not used, the COM/CRA is responsible for notifying Clinical QA upon discovery that a PQC has occurred.

Upon receipt of the EDC notification, the COM/CRA will contact the study site to collect additional information which will include:

- Date the complaint was received/recorded in the EDC System (Date of Sponsor Awareness)
- Who received the complaint

- Study number
- Clinical site information (contact name, site ID, telephone number)
- Lot number(s)
- Unique Subject Identifier(s)
- Indication of who first observed complaint (site personnel or subject)
- OD/OS indication, along with whether the lens was inserted
- Any related AE number if applicable
- Detailed complaint description (scheduled/unscheduled visit, wear time, symptoms, resolution of symptoms, etc.)
- Eye Care Provider objective (slit lamp) findings if applicable
- Confirmation of product availability for return (and tracking information, if available), or rationale if product is not available for return [REDACTED]

Once a complaint is received, it will be assessed by the COM, CRA, or trained site personnel to determine if it is an Adverse Event/Serious Adverse Event (AE/SAE). If the complaint results in an AE/SAE, the COM/CRA, or trained site personnel will follow Section 13 of this protocol. If the AE/SAE was potentially the result of a product quality related deficiency, these procedures also apply and will be executed in parallel.

In some cases, a PQC form may be generated in EDC by the site in error. In this event, the PQC forms will be marked “Intentionally Left Blank” or “ILB”. Justification for ILB must be documented.

## 13. ADVERSE EVENTS

### 13.1. Definitions and Classifications

**Adverse Event (AE)** – An AE is “any untoward medical occurrence, unintended disease or injury, or untoward clinical signs (including abnormal laboratory findings) in subjects, users or other persons, whether or not related to the investigational medical device.

*Note 1 to entry:* This definition includes events related to the investigational medical device or the comparator.

*Note 2 to entry:* This definition includes events related to the procedures involved.

*Note 3 to entry:* For users or other persons, this definition is restricted to events related to investigational medical devices.”

An AE includes any condition (including a pre-existing condition) that:

1. Was not present prior to the study, but appeared or reappeared following initiation of the study
2. Was present prior to the study, but worsened during the study. This would include any condition resulting from concomitant illnesses, reactions to concomitant medications, or progression of disease states
3. Pregnancy must be documented as an adverse event and must be reported to the clinical monitor and to the Sponsor immediately upon learning of the event

**Serious Adverse Event (SAE)** – An SAE is any untoward medical occurrence that:

- Results in death
- Is life threatening
- Requires in-patient hospitalization or prolongation of existing hospitalization
- Results in persistent or significant disability/incapacity (e.g., a sight threatening event, a significant persistent or permanent change, impairment, damage, or disruption to the subject's body)
- Is a congenital anomaly/birth defect, or
- Requires intervention to prevent permanent damage (the use of the test article resulting in a condition which requires medical or surgical intervention to preclude permanent impairment of the body structure or a body function). Important medical events that may not result in death, be life-threatening, or require hospitalization may be considered an SAE when, based upon appropriate medical judgment, they may jeopardize the patient or subject and may require medical or surgical intervention to prevent one of the outcomes listed in the above definition

Diagnoses and conditions that are considered Ocular Serious Adverse Events include, but not limited to:

- Microbial Keratitis (MK)
- Iritis (including cells in the anterior chamber)
- Permanent decrease in best spectacle corrected visual acuity equivalent to 2 acuity lines or greater
- Central Corneal Opacity
- Central Corneal Neovascularization
- Uveitis
- Endophthalmitis
- Hypopyon
- Hyphemia
- Penetration of Bowman's Membrane
- Persistent Epithelial Defect
- Limbal cell Damage leading to Conjunctivalization

**Significant Adverse Events** – Those events that are usually symptomatic and warrant discontinuation (temporary or permanent) of the test article (excluding Serious Adverse Events).

Diagnoses and conditions that are considered Ocular Significant Adverse Events include, but not limited to the following:

- Contact Lens Induced Peripheral Ulcer (CLPU)
- Significant Infiltrative Events (SIE)
- Superior Epithelial Arcuate Lesions (SEALs)
- Any Temporary Loss of > 2 Lines of BSCVA
- Other grade 3 or higher corneal findings, such as abrasions or edema
- Non-contact lens related corneal events - e.g. Epidemic Keratoconjunctivitis (EKC)
- Asymptomatic Corneal Scar

- Any corneal event which necessitates temporary lens discontinuation > 2 weeks

**Non-Significant Adverse Events** – Those conditions that are usually asymptomatic and usually do not warrant discontinuation (temporary or permanent) of the test article. However, the Investigator may choose to treat as a precautionary measure.

Diagnoses and conditions that are considered Ocular Non-Significant Adverse Events include, but not limited to the following:

- Non-significant Infiltrative Event (NSIE)
- Contact Lens Papillary Conjunctivitis (CLPC)
- Superficial Punctate Keratitis (SPK)
- Conjunctivitis: Bacterial, Viral, Allergic
- Blepharitis
- Meibomianitis
- Contact Dermatitis
- Localized Allergic Reactions
- Any corneal event not explicitly defined as serious or significant adverse event, which necessitates temporary lens discontinuation < 2 weeks

**Adverse Device Effect (ADE)** – An ADE is an “adverse event related to the use of an investigational medical device.

*Note 1* to entry: This definition includes adverse events resulting from insufficient or inadequate instructions for use, deployment, implantation, installation, or operation, or any malfunction of the investigational medical device.

*Note 2* to entry: This definition includes any event resulting from use error or from intentional misuse of the investigational medical device.”

**Unanticipated Adverse Device Effect (UADE)** – Any serious adverse effect on health or safety or any life-threatening problem or death caused by, or associated with, the test article, if that effect, problem, or death was not previously identified in nature, severity, or degree of incidence in the investigational plan, Investigator’s Brochure or protocol, or any other unanticipated serious problem associated with the test article that relates to the rights, safety and welfare of subjects.

### 13.2. Assessing Adverse Events

In conjunction with the medical monitor, the Investigator will evaluate adverse events to ensure the events are categorized correctly. Elements of categorization will include:

- Seriousness/Classifications (see definition in Section 13.1)
- Causality or Relatedness – i.e. the relationship between the test article, study treatment or study procedures and the adverse event (not related; unlikely related; possibly related; related - see definition in Section 13.2.1)
- Adverse Event Severity – Adverse event severity is used to assess the degree of intensity of the adverse event (mild; moderate; severe for all events - see definition in Section 13.2.2)

- Outcome – not recovered or not resolved; recovering or resolving; recovered or resolved with sequelae; recovered or resolved; death related to adverse event; unknown
- Actions Taken – none; temporarily discontinued; permanently discontinued; other

### 13.2.1. Causality Assessment

**Causality Assessment** – A determination of the relationship between an adverse event and the test article. The test article relationship for each adverse event should be determined by the investigator using these explanations:

- Not Related- An adverse event that is not related to the use of the test article, study treatment or study procedures
- Unlikely Related – An adverse event for which an alternative explanation is more likely, e.g. concomitant treatment, concomitant disease(s), or the relationship of time suggests that a causal relationship is not likely
- Possibly Related – An adverse event that might be due to the use of the test article, or to the study treatment or study procedures. An alternative explanation, e.g. concomitant treatment, concomitant disease(s), is inconclusive. The relationship in time is reasonable. Therefore, the causal relationship cannot be excluded
- Related – An adverse event that is listed as a possible adverse effect (device) or adverse reaction (drug) and cannot be reasonably explained by an alternative explanation, e.g. concomitant treatment of concomitant disease(s). The relationship in time is very suggestive, e.g. it is confirmed by de-challenge and re-challenge

### 13.2.2. Severity Assessment

**Severity Assessment** – A qualitative assessment of the degree of intensity of an adverse event as determined by the Investigator or reported to him/her by the subject. The assessment of severity is made irrespective of test article, study treatment or study procedure relationship or seriousness of the event and should be evaluated according to the following scale:

- Mild – Event is noticeable to the subject, but is easily tolerated and does not interfere with the subject's daily activities
- Moderate – Event is bothersome, possibly requiring additional therapy, and may interfere with the subject's daily activities
- Severe – Event is intolerable, necessitates additional therapy or alteration of therapy and interferes with the subject's daily activities

### 13.3. Documentation and Follow-Up of Adverse Events

The recording and documenting of adverse events (ocular and non-ocular) begins when the subjects are exposed to the test article, study treatment or study procedure. Adverse events reported before the use of test article, start of study treatment, or study procedures will be recorded as medical history. However, if the condition deteriorates at any time during the study it will be recorded and reported as an AE. Untoward medical events reported after the subject's exit from the study will be recorded as adverse events at the discretion of the Investigator.

Upon finding an adverse event, the Principal Investigator will document the condition in the subject record and in the eCRFs. He/she will complete the Adverse Event /eCRF.

Complete descriptions of all adverse events must be available in the subject record. All Adverse Events including local and systemic reactions not meeting the criteria for “serious adverse events” shall be captured on the appropriate case report form or electronic data system. All adverse events occurring while the subject is enrolled in the study must be documented appropriately regardless of relationship.

It is the Investigator’s responsibility to maintain documentation of each reported adverse event. All adverse events will be followed in accordance with applicable licensing requirements. Such documentation will include the following:

- Adverse event (diagnosis not symptom)
- Drawings or photographs (where appropriate) that detail the finding (e.g., size, location, and depth, etc.)
- Date the clinical site was notified
- Date and time of onset
- Date and time of resolution
- Adverse event classification, severity, and relationship to test articles, as applicable
- Treatment regimen instituted, including concomitant medications prescribed, in accordance with applicable licensing requirements
- Any referral to another health care provider if needed
- Outcome, ocular damage (if any)
- Likely etiology
- Best corrected visual acuity at the discovery of the event and upon conclusion of the event

In addition, if an infiltrate(s) is present, he/she will complete the Corneal Infiltrate Assessment eCRF. Where necessary, a culture of the corneal lesion will be collected to determine if the infection is microbial in nature. If cultures are collected, the date of culture collection and laboratory utilized will be recorded.

Changes in the severity of an AE shall be documented to allow an assessment of the duration of the event at each level of intensity to be performed. Adverse events characterized as intermittent require documentation of the onset and duration of each episode. Changes in the assessment of relationship to the Test Article shall also be clearly documented.

Subjects who present with an adverse event shall be followed by the Investigator, within licensure, until all signs and symptoms have returned to pre-treatment status, stabilized, or been satisfactorily resolved. If further treatment beyond licensure is required, the patient will be referred to the appropriate health care provider. The Investigator will use his/her clinical judgment as to whether a subject reporting with an adverse event will continue in the study. If a subject is discontinued from the study, it will be the responsibility of the Investigator to record the reason for discontinuation. The Investigator will also document the adverse event appropriately and complete the Adverse Event eCRF. Any subjects with ongoing adverse events related to the test article, study treatment or study procedures, as of the final study visit date, should be followed to resolution of the adverse event or until referral to an appropriate health care provider, as recommended by the Investigator. Non-ocular adverse events that are

not related to the test article, study treatment, or study procedures may be recorded as “ongoing” without further follow-up.

### **13.4. Reporting Adverse Events**

The Investigator will notify the Sponsor of an adverse event by e-mail, facsimile, or telephone as soon as possible and no later than 24 hours from discovery for any serious /significant adverse events, and 2 days from discovery for any non-significant adverse event. In addition, a written report will be submitted by the Principal Investigator to the IEC/IRB according to their requirements (Section 13.4.2). The report will comment whether the adverse event was considered to be related to the test article, study treatment or study procedures.

#### **13.4.1. Reporting Adverse Events to Sponsor**

##### **Serious/Significant Adverse Events**

The Investigator will inform the sponsor of all serious/significant adverse events occurring during the study period as soon as possible by e-mail, fax, or telephone, but no later than 24 hours following discovery of the event. The Investigator is obligated to pursue and obtain information requested by the Sponsor in addition to that information reported on the eCRF. All subjects experiencing a serious/significant adverse event must be followed up and all outcomes must be reported.

In the event of a serious/significant adverse event, the Investigator must:

- Notify the Sponsor immediately
- Obtain and maintain in the subject’s records all pertinent medical information and medical judgment for colleagues who assisted in the treatment and follow-up of the subject
- Provide the Sponsor with a complete case history which includes a statement as to whether the event was or was not related to the use of the test article
- Notify the IEC/IRB as required by the IEC/IRB reporting procedure according to national regulations

##### **Unanticipated (Serious) Adverse Device Effect (UADE)**

In the event of an Unanticipated (Serious) Adverse Device Effect (UADE), the Investigator will submit a report of the UADE to the Sponsor and IEC/IRB as soon as possible, but no later than 24 hours after the Investigator first learns of the effect. This report is in addition to the immediate notification mentioned above.

The Sponsor must conduct an evaluation of the UADE and must report the results of the evaluation to FDA, the IEC/IRB and participating Investigators within 10 working days after the Sponsor first receives notification of the effect.

##### **Non-Serious Adverse Events**

All non-serious adverse events, including non-serious adverse device effects, will be reported to the sponsor by the Investigator no later than 2 days from discovery.

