## **4. STUDY DESIGN AND RATIONALE**

### **4.1. Description of Study Design**

The study design is controlled, randomized, subject-masked, 3 treatment ×3 period, non-dispensing, contralateral study.

After a pre-screening assessment, eligible subjects will be invited to attend an initial visit. Subjects will be prescreened using the CLDEQ-8 questionnaire with their habitual lenses and those who are classified as symptomatic (CLDEQ-8 score of 20-37) will be scheduled for Visit 1.

At study Visit 1, subjects will be consented and screened for inclusion/exclusion criteria. If a subject is found to meet all eligibility criteria, they will be asked to attend Visit 2 which will take place on a different day. Subjects will be asked to wear their contact lenses early in the morning (at home) on the day of Visit 2 and to rate subjective comfort on a paper VAS scale immediately prior to lens application and 5 minutes post-application. They will be asked to attend the study visit having worn their habitual lenses for  $14 \pm 2$  hours. At Visit 2, one of three areas (upper lid margin, lower lid margin or cornea) will be anesthetized on one eye, whilst the fellow eye will receive a saline placebo treatment in the same location. The ocular surface region and treatment will be randomly assigned. The right eye will always be assessed first. Subjective comfort scores (VAS scale) will be collected prior to and following the treatment on each eye (5 and 10 minutes post-treatment). On the day of corneal treatment, VAS comfort scores will also be collected immediately after lens removal prior to treatment application. Subjects will be asked to return for Visit 3 on a different study day, again having worn their lenses for  $14 \pm 2$  hours and the same procedures as at Visit 2 will take place. The same procedures as for Visit 3 will be repeated for Visit 4. Visits 2-4 will be scheduled 1-14 days apart.

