## **4.2. Study Design Rationale**

Crossover designs are a well-established cost-effective study design in which subjects are exposed to multiple treatments during different time periods. The study design allows for a direct and meaningful comparison of three anesthesia treatments. A minimum period of 24 hours between visits (i.e. between each treatment) was implemented to reduce any potential carry-over effect that may bias the results.

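### Section 13.4.1 gives all non-serious adverse events 2 days to reach the sponsor, so significant events, which are non-serious by definition and due within 24 hours, carry two conflicting deadlines.

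*Combined protocol and SAP*

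**What the plan says.** Section 13.1 sorts adverse events into serious, significant and non-significant. Significant events are those that are usually symptomatic and "warrant discontinuation (temporary or permanent) of the test article (excluding Serious Adverse Events"; the closing words put serious events outside the class. The ocular examples include contact-lens peripheral ulcer, significant infiltrative events, SEALs, other corneal findings of grade 3 or above such as abrasions, and temporary loss of more than two lines of best spectacle-corrected acuity.

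Reporting times to the sponsor are then given in three places:

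- Section 13.4, the general rule: "no later than 24 hours from discovery for any serious /significant adverse events, and 2 days from discovery for any non-significant adverse event".
- Section 13.4.1, Serious/Significant Adverse Events: as soon as possible, "but no later than 24 hours following discovery of the event". The list of duties below it adds "Notify the Sponsor immediately".
- Section 13.4.1, last part, under the non-serious heading, reads: "All non-serious adverse events, including non-serious adverse device effects, will be reported to the sponsor by the Investigator no later than 2 days from discovery". No exception is made for significant events.

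**The concern.** The 2-day class is called *non-significant* in Section 13.4 and *non-serious* in Section 13.4.1. Under the protocol's own definitions these are different sets: the second contains the first and, in addition, every significant event.

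The non-serious paragraph is a headed rule in the section a site would open to look up a deadline. *Non-serious* also has a natural reading in this protocol, because Section 13.3 refers to events that do not meet the serious criteria as a group of their own. A coordinator with a grade 3 corneal abrasion that is not an SAE could reasonably look under the non-serious heading and find 2 days.

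What is at stake is prompt and auditable safety reporting. Section 13.2 has the investigator categorise events together with the medical monitor, and Section 11 has the sponsor evaluate all adverse events. Both wait on notification. Compliance also cannot be audited cleanly when one event has two written limits.

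**Working it through.** No power, alpha or sample-size figure is involved, so the check is a cross-reading of definitions against deadlines.

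**Step 1: is a significant event non-serious?** Section 13.1 takes serious events out of the significant class. An event classed as significant is therefore not serious, and it belongs to the set named in the last part of 13.4.1.

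**Step 2: apply each rule to each class.**

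| Class in 13.1 | Serious? | 13.4 | 13.4.1, Serious/Significant | 13.4.1, Non-Serious |
|---|---|---|---|---|
| Serious | Yes | 24 h | 24 h | not covered |
| Significant | No | 24 h | 24 h | **2 days** |
| Non-significant | No | 2 days | not covered | 2 days |

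The serious and non-significant rows each give one answer. The significant row gives two. The instruction to notify immediately does not add a further conflict, because it sits under the same heading as the 24-hour limit and is compatible with it as an outer bound.

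**Step 3: size of the disagreement.** Taking 2 days as 2 × 24 = 48 hours, the limits differ by 48 − 24 = 24 hours. That is the most by which a report timed by the non-serious paragraph alone, and still inside its limit, could overrun the other two rules.

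**Step 4: effect of aligning the term.** If the last column covered only non-significant events, its entry in the significant row would become *not covered*. All three classes would then have one deadline each, and no class would be left without one.

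**The case against.** The strongest reply is that this is a slip of wording with a clear answer. Section 13.4 is the parent section, and both it and the Serious/Significant part of 13.4.1 name the significant class expressly. Section 13.4 confines the longer limit in so many words: "and 2 days from discovery for any non-significant adverse event". Every limit is an upper bound, so a report made within 24 hours satisfies all three places. This stands: on the whole document the binding limit for a significant event is 24 hours. A reader might infer that a site following the non-serious paragraph is compliant. It is not. Reporting a significant event at 48 hours meets that paragraph but breaches the other two.

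A reader might also infer that the conflict lets a subject be treated again before the sponsor has to be told, given "Visits 2-4 will be scheduled 1-14 days apart" in Section 4.1 and "A minimum period of 24 hours between visits (i.e. between each treatment) was implemented" in Section 4.2. The arithmetic looks suggestive. For an event found at a treatment visit (hour 0), the earliest next visit is hour 24, the 24-hour limit is also hour 24, and the 2-day limit is hour 48. The documents do not support the inference, for three reasons:

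- The 24-hour rules continue to apply, so the gap appears only if the non-serious paragraph is read in isolation.
- Nothing makes sponsor notification a condition of the next treatment. Repeat treatment is governed elsewhere: adverse-event review and slit lamp examination precede treatment (steps 2.4 and 2.9). Section 8.2 withdraws subjects for a significant event that stops lens wear, a corneal infiltrative event or loss of eligibility. Section 13.3 otherwise leaves continuation to the investigator's judgment.
- For an event discovered *h* hours after a visit, with *h* above 0, even the 24-hour limit falls at hour 24 + *h*, after the earliest next visit. The overlap in wording is not what creates that gap.

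It is also fair to say that this is a single-site study and that the point touches no analysis. None of this removes the contradiction. A headed rule that has to be overridden by reading its parent section is still wrong as written.

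**Conclusion.** The contradiction is real and follows from the protocol's own definitions. One of the three event classes, the significant one, has both a 24-hour and a 2-day reporting limit. The practical size is a possible delay of up to 24 hours in telling the sponsor, at a site that relies on the non-serious paragraph alone. This rests on applying the Section 13.1 definitions literally and on counting 2 days as 48 hours, since the protocol does not say how days are counted.

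The point goes no further than safety-reporting wording. It is a minor to moderate inconsistency that should be corrected because it concerns an operative deadline and costs almost nothing to put right.

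**What to change.** Reconcile Section 13.4 and the two parts of Section 13.4.1 so that a significant event has a single reporting deadline. The narrowest edit is in the last part of 13.4.1: replace *non-serious* with *non-significant* in the heading and at both places in the sentence, once for adverse events and once for adverse device effects. Changing only the first use in the sentence would leave a significant, non-serious device effect under the 2-day limit, and the overlap would persist for those events. *Non-significant* is already a defined class in 13.1, so serious events would not be drawn into the longer limit.

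The cost is three word changes and a reminder to the site. If the protocol has already been approved, the change goes to the IEC/IRB as an amendment under Section 18.3. No change to data collection or analysis is needed.
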